Specific Aim 5: Explore modifiable factors that may impact physical activity, as assessed with step activity monitors, including comorbidities, balance-confidence, fatigue, sleep disturbance, balance, functional lower extremity strength, functional mobility and agility among adults with (n=20) and without a unilateral below-the-knee amputation (n=20).

Hypotheses: For both adults with and without a below-the-knee amputation (after controlling for covariates):

H5a: Comorbidities: Average daily step counts will be significantly lower for adults with greater comorbidity burden, as assessed with the Cumulative Illness Rating Scale.

H5b: Balance-Confidence: Average daily step counts will be significantly lower for adults who have lower balance-confidence per the Activities-Specific Balance Confidence Scale.

H5c: Fatigue: Average daily step counts will be significantly lower for adults who indicate fatigue on the PROMIS-29, as compared to those who do not indicate fatigue.

H5d: Sleep Disturbance: Average daily step counts will be significantly lower in adults who indicate sleep disturbance on the PROMIS-29, as compared to those who do not indicate sleep disturbance.

H5e: Balance: Average daily step counts will be significantly lower in adults with decreased Functional Reach Test distance and adults who are unable to maintain balance for 30 seconds during m-CTSIB conditions 3 and 4 (foam, eyes open and foam, eyes closed).

H5f: Functional Lower Extremity Strength: Average daily step counts will be significantly lower in adults with decreased lower extremity functional strength, defined as slower 5 Times Repeated Chair Rise times.

H5g: Functional Mobility: Average daily step counts will be significantly lower in adults with decreased functional mobility, defined as increased L-test times.

H5h: Agility: Average daily step counts will be significantly lower in adults with worse agility as indicated by slower Four Square Step Test times and Figure-of-8 Walk test times.

Specific Aim 6: Explore the relationship between gait asymmetry, as quantified by spatio-temporal and 3D kinematic parameters (e.g. cadence, stance and swing time, step length, and joint position), and energy expenditure among inactive adults with a single, below-the-knee amputation (n=20) during treadmill walking at self-selected and fast walking speeds.

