Hypothesis: Energy expenditure will be greater among inactive adults with a single, below-the knee amputation who demonstrate greater side-to-side differences in walking pattern during treadmill walking at both self-selected and fast walking speeds ($p<0.05$).

Specific Aim 7: Compare side-to-side differences in walking pattern (e.g. speed, step length, and joint position) between inactive adults with a single, below-the-knee amputation (n=20) and age-matched controls (n=20) during over-ground and treadmill walking using the APDM Mobility Lab software.

Hypothesis: For both over-ground and treadmill walking conditions, inactive adults with a single, below-the knee amputation will demonstrate greater side-to-side differences in walking pattern compared to age-matched controls ($p<0.05$).

Specific Aim 8: Explore the relationship between inspiratory muscle endurance, as quantified by an individual's sustained maximal inspiratory pressure (SMIP), and energy expenditure among inactive adults with a single, below-the-knee amputation (n=20) during treadmill walking at self-selected and fast walking speeds.

Hypothesis: Energy expenditure will be greater among inactive adults with a single, below-the knee amputation who demonstrate decreased SMIP values (p<0.05).

Specific Aim 9: Compare differences in inspiratory muscle endurance (measured by sustained maximal inspiratory pressure, or SMIP) between inactive adults with a single, below-the-knee amputation (n=20) and age-matched controls (n=20) using the PrO₂ device.

Hypothesis: Inactive adults with a single, below-the knee amputation will demonstrate decreased SMIP values compared to age-matched controls (p<0.05).

Specific Aim 10: Compare differences in inspiratory muscle endurance (measured by sustained maximal inspiratory pressure, or SMIP) between inactive adults with a single, below-the-knee amputation who have low back pain compared to those who do not report pain.

Hypothesis: Inactive adults with a single, below-the knee amputation who experience low back pain will demonstrate decreased SMIP values compared to individuals with a single, below-the-knee amputation who do not have pain (p<0.05).

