Participants will be fit with a mobile gait analysis system (APDM Mobility Lab) that will assess gait symmetry during the over-ground and treadmill walking tests that follow. Participants will be fit with APDM Mobility Lab sensors at the following locations: sternum, posterior surface of both wrists, lumbar spine, anterior surface of both thighs, anterior surface of both lower legs (and/or the sound lower leg and the prosthetic leg), and the dorsal surface of both feet (and/or the sound foot and prosthetic foot). This will take approximately 5 minutes.

The APDM software will be used to collect spatio-temporal measurements, such as stride length and velocity, as well as three-dimensional kinematic measurements, including joint position and acceleration throughout the gait cycle and maximal toe clearance during the swing phase of gait. Information regarding trunk sway and arm swing will also be collected.

Participants will also be fit with a Polar heartrate monitor, worn around the chest on the skin, to allow vital sign monitoring during the over-ground and treadmill walking conditions. The examiner will wear the wristwatch monitoring unit during the walking bouts for ease of monitoring.

Gait Speed Pre- and Post-Walking Conditions Assessment

We will use a computerized walkway system (GaitRite) to obtain self-selected (3 trials) and fast-walking speeds (3 trials) as well as other spatiotemporal parameters of gait immediately before and after each walking condition. APDM sensor data collection will also occur during self-selected and fast walking trials over the GaitRite system. By comparing pre- and post-walking gait speeds, we may be able to determine if the participant experienced fatigue during the walking bout. This will take <3 minutes per collection; there will be 4 collections total.

Metabolic Cost Testing Procedures. Participants will have their metabolic energy expenditure (i.e. oxygen consumption) measured as they walk at various speeds within the Department of Physical Therapy. Individuals with a unilateral transtibial amputation will complete the following two tests in a randomized order (controls will complete the tests in the same order as their matched participant with a unilateral transtibial amputation):

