Specific Aim 1: To determine reliability, intra-class correlation coefficients (ICCs) with 95% confidence intervals (CIs) will be calculated to evaluate test-retest reliability of physical activity

questionnaires. To evaluate validity between the self-report questionnaire data and activity-monitor obtained data that is continuous (e.g. steps/day, total activity in minutes/day), we will use ICCs with 95% CIs. We will quantify the relationship between the self-report data and activity-monitor data using Spearman's correlation coefficients. Interpretation will be as follows: $p \leq .25$ =weak correlation, $p=.26\text{--}.49$ =low correlation, $p=.50\text{--}.69$ =moderate correlation, $p \geq .70$ =high correlation.

Specific Aim 2: We will use receiver operating characteristic (ROC) curves to determine the minimal speed and cadence that corresponds to an oxygen consumption value of 10.5 mL/kg/min (i.e. 3.0 METs), as this has been identified by the World Health Organization as 'moderate intensity' activity.¹⁰

Specific Aims 3 and 6-10: We will use a MANOVA/MANCOVA to evaluate between-group differences with follow-up ANOVAs/ANCOVAs as appropriate ($p \leq 0.05$).

Specific Aims 4/5: Regression models will be used to explore relationships between energy expenditure (or average daily step counts) and each of the modifiable factors of interest, while controlling for relevant non-modifiable covariates, e.g. age, residual limb length.

Reported

Dissemination of results will occur through conference presentations and manuscript publications in peer-reviewed journals.

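### Aim 7 follows a MANOVA with unadjusted ANOVAs over an open list of gait-asymmetry parameters, so findings on individual parameters are not protected once any parameter truly differs

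*Combined protocol and SAP*

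**What the plan says.** Section 5 (Research Abstract), Specific Aim 7, is to "Compare side-to-side differences in walking pattern (e.g. speed, step length, and joint position) between inactive adults with a single, below-the-knee amputation" and age-matched controls, 20 per group. Its hypothesis is tested at p<0.05 and reads: "For both over-ground and treadmill walking conditions, inactive adults with a single, below-the knee amputation will demonstrate greater side-to-side differences". The three parameters are examples. Neither a full list, a count nor a deciding measure is given anywhere.

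Section 6 (Procedures), Pre-Walking Set-Up, shows how many parameters could be drawn on. Besides stride length and velocity, the sensors give "three-dimensional kinematic measurements, including joint position and acceleration throughout the gait cycle and maximal toe clearance during the swing phase of gait", and trunk sway and arm swing are also collected.

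Section 10 (Data) gives Aims 3 and 6-10 a single method: "We will use a MANOVA/MANCOVA to evaluate between-group differences with follow-up ANOVAs/ANCOVAs as appropriate", at p ≤ 0.05. No multiplicity adjustment appears in the document. Section 5 describes Aims 4 and 5 as exploratory and says nothing of the kind about Aim 7.

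**The concern.** A MANOVA used as a gate limits false findings only when none of the parameters differs between groups. Aim 7 predicts a difference. If that prediction is right for even one parameter, a significant MANOVA is the correct result, and it then licenses a separate 0.05 test of every other parameter. Nothing limits the number of those tests, because the list is open.

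What is at stake is the parameter-level message: which side-to-side differences distinguish people with an amputation from controls. A report could name a specific asymmetry that is a chance finding, and a reader could not tell how many parameters had been tried.

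**Working it through.** **Inputs from the plan.** Groups of 20 and 20 (Aim 7; the Section 6 overview gives 22 and 20); alpha 0.05 per follow-up test; three named examples; two walking conditions. Taken literally, one of the three, speed, is not a side-specific quantity, so three is a nominal count.

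**Inputs not in the plan, assumed.** Number of parameters 3 to 8; equal correlation between parameters of 0 to 0.5; one truly different parameter per condition, by 0.8 to 1.5 SD; two-sided tests. The plan states no familywise error rate and no power calculation, so there is no figure of its own to reproduce.

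**Step 1: upper guide without the gate.** With m truly null parameters, independent and each tested at 0.05, the chance of at least one false finding is 1 − 0.95^m.
- Three examples, one condition, one true difference: m = 2, 1 − 0.9025 = 9.8%.
- Three examples, two conditions, the same parameter differing in both: m = 4, 1 − 0.8145 = 18.5%.
- Eight parameters, one condition, one true difference: m = 7, 1 − 0.6983 = 30.2%.

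**Step 2: with the gate.** Simulated studies at 20 v 20 used Hotelling's T² at 0.05 (the two-group MANOVA) and then, if significant, t tests at 0.05 (the two-group ANOVAs). A study counts as false if any truly null parameter is declared different. With one true 1.5 SD difference per condition:
- three parameters, one condition: about 9-10%;
- three parameters, both conditions: about 17-18%. As a check, two independent conditions at 9% each give 1 − 0.91² = 17.2%;
- eight parameters, one condition: about 23% at correlation 0.5 and about 28% at correlation 0.

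**Step 3: how often the gate opens.** One true difference, one condition:

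| Parameters, correlation | True difference | MANOVA significant | At least one false parameter |
|---|---|---|---|
| 6, 0 | 0.8 SD | 37% | 14.0% |
| 6, 0 | 1.0 SD | 55% | 17.7% |
| 6, 0 | 1.5 SD | 92% | 22.4% |
| 8, 0 | 0.8 SD | 30% | 15.1% |
| 8, 0 | 1.0 SD | 47% | 20.3% |
| 8, 0 | 1.5 SD | 87% | 28.7% |
| 8, 0.5 | 0.8 SD | 54% | 16.9% |
| 8, 0.5 | 1.0 SD | 77% | 20.0% |
| 8, 0.5 | 1.5 SD | 99% | 23.1% |

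Using 22 v 20 changes little: six parameters, correlation 0, 1.5 SD gives 21.8% against 22.4%.

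**Step 4: no true difference.** If no parameter differs, any false finding within one MANOVA-plus-ANOVA sequence occurs in about 4-5% of studies. Here the gate works as intended.

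**Step 5: direction.** If only significant results in the predicted, greater direction count, the rates are about half: roughly 5% for three parameters in one condition (9-10% ÷ 2) and 12-14% for eight (23-28% ÷ 2).

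**Step 6: Holm.** Holm over the parameters at 0.05 gave about 3-5% in every setting.

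**The case against.** The strongest defence is that the aim-level conclusion is sound. Wherever the error is inflated, people with an amputation really are more asymmetric in something, so Aim 7's general hypothesis is true; and where nothing differs, the gate holds. This stands. The inflation concerns which parameters are named, not whether any asymmetry exists.

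A second defence is that the hypothesis predicts greater asymmetry in both conditions. If the same parameter had to be significant in both, and in that direction, a false parameter would appear in only 0.3-5.6% of studies (3 to 10 parameters, correlation 0 to 0.8, cross-condition correlation assumed 0.3 to 0.7). The plan states no such rule, so this is one possible reading and not a protection the plan provides. Writing the rule down would help.

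Three stronger readings are tempting, and the documents do not support them:
- A reader might infer that about a quarter of such studies would report a false asymmetry. That needs more parameters than Aim 7 names, or near-independence across all tests. For the three named examples in one condition the figure is 9-10%.
- A reader might infer that one true difference is enough to open the gate. At 20 per group it often is not, as step 3 shows.
- A reader might extend the figures to Aim 6. Its wording is "Explore the relationship between gait asymmetry, as quantified by spatio-temporal and 3D kinematic parameters" and energy expenditure, within the amputee group only. It has no second group, so the two-group MANOVA results do not describe it. Section 10 nevertheless assigns Aim 6 the between-group method, which does not match its question. Aim 6 also opens with the verb explore, so it is less clearly confirmatory than Aim 7.

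**Conclusion.** The concern holds for Aim 7 at the level of individual parameters. An open list, two walking conditions and follow-up ANOVAs at an unadjusted 0.05 leave parameter-specific findings unprotected once at least one parameter truly differs.

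Under the step 2 assumptions, the chance of at least one false parameter is about twice the nominal 5% for the three named examples in one condition. It is more than three times nominal over both conditions, and about 23-28% if eight parameters are extracted. It is lower with smaller true effects and about half if only the predicted direction counts. The only counts that come from the plan are the three examples and the two conditions; the eight parameters, the correlations and the effect sizes are assumptions. This is a gap the plan should close, not a threat to the aim as a whole.

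**What to change.** For Aim 7, name one deciding side-specific measure, for example step-length asymmetry, or a short closed list such as step length, stance time and swing time. In Section 10, replace the open follow-up step for this aim with Holm-adjusted comparisons over that list and both walking conditions. Report every other sensor parameter with a 95% confidence interval under an explicit exploratory label.

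For Aim 6, use the same named measure or list and label the other parameters exploratory.

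The cost is a few sentences of analysis text and no new measurement. Power for each individual parameter falls slightly, and there are fewer parameters on which a claim can be made.

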6. PROCEDURES

Describe all procedures involving human subjects for this protocol. Include copies of all surveys and research measures.

Overview: We propose to conduct a cross-sectional study of 22 adults with a unilateral transtibial amputation as compared to 20 sex-, age- (+/- 5 years), and body mass index- (+/- 5 kg/m²) matched controls. This one-time session is projected to take ~ 2hours on-site at the University of Delaware on the STAR campus within the Department of Physical Therapy.

Once contact is made with potential participants, inclusion and exclusion criteria will be examined in 2 phases, first over the telephone using a structured questionnaire, and then on-site by a research team member to validate inclusion and exclusion criteria obtained by telephone. Prior to telephone screening, verbal consent will be obtained from the participant. The on-site screening will occur after individuals have signed the informed consent.

All Participants will complete a series of questionnaires that will be sent via a mailing packet prior to the on-site evaluation. Questionnaires will take about 30 minutes to complete. Questionnaires included in this Mailing Packet will be the:

1. Demographics Mailing Sheet: Will provide pertinent demographic information necessary for characterizing and matching participants (i.e. age, sex).
2. Medical History Checklist: We would like to have participants complete this questionnaire as it will improve the efficiency and accuracy of the Cumulative Index Rating Scale.⁵⁰ Further, it will alert the physical therapist to any relevant problems that should be consider during physical performance testing and when testing energy expenditure during the 2 walking conditions.
3. Medication Sheet: Medication review using this sheet prior to physical performance testing and testing of energy expenditure during the 2 walking conditions will enhance patient safety and allow for appropriate interpretation of vital sign responses. This sheet will also allow increased efficiency and accurate scoring for the Cumulative Illness Rating Scale regarding comorbidities.⁵⁰
4. Activities Specific Balance Confidence Scale (ABC): The ABC is a valid³² 16-item

questionnaire where individuals rate how confident they are that they will not lose their balance or become unsteady with various ambulatory activities on a 0-100% scale, where 0=no confidence and 100%=complete confidence.²⁷

5. Patient-Reported Outcomes Measurement Information System (PROMIS-29): The PROMIS-29 is a subset of the PROMIS assessment of self-reported health²⁹ that measures quality of life based on physical function, pain interference, fatigue, sleep disturbance, anxiety, depression, and social participation.^{30,31} Individuals with lower-limb loss have been shown to score significantly lower on physical function, pain interference, and participation in social role subscales when compared to individuals without lower limb amputation.³¹
6. International Physical Activity Questionnaire – Long Form (IPAQ)*: The questionnaire, designed for adults ages 18-65, consists of 31 items assessing physical activity in four domains: transportation, work, household and gardening tasks, and leisure time.³³ It is a valid and reliable measure of self-reported physical activity level in healthy adults³⁴; however, psychometric properties have not been established for use in individuals with lower-limb amputation. We will use this measure to compare self-reported physical activity levels to objective physical activity characteristics obtained from 7-days of monitoring via step-activity monitors.
7. Incidental and Planned Exercise Questionnaire-past week*: This questionnaire has 10 items that ask about exercise type, intensity, and duration in the past week.

*These 2 questionnaires will be provided to the participant at the end of the on-site evaluation. Participants will be asked to re-complete these questionnaires at the end of their 7 days of activity monitoring and return in the envelope with the step activity monitor and activity monitor log. It is projected that re-completion of these 2 questionnaires will take < 10 minutes.

Individuals with lower-limb amputations will also complete the following:

8. Houghton Scale of Prosthetic Use⁴⁸: The questionnaire has 4 items related to wear duration, use, and perceived stability.²⁸ Total scores range from 0-12 with higher scores indicating better function.²⁸ Scores $\geq 9/12$ suggest the individual is a community-ambulator. This questionnaire will help to characterize the participants with limb-loss in our sample.

Questionnaires completed by participants who opt not to participate in the study (i.e. do not complete the informed consent) or who are deemed ineligible on-site will be shredded and placed in the trash (or given back to the participant to take home). This information will not be retained by the research staff. Informed consent documents will be retained in a locked file available only to research personnel. Participants will be given a copy of the informed consent for their records. Individuals with lower-limb amputations will also be asked to sign a HIPPA form. A copy of this form will be given to these research participants with a lower-limb amputation. The HIPPA form will request that the participant agree to share their medical records to allow determination of their current prosthetic components, to control for this factor during the data analysis. Specifically, we would like to control for the type of foot, passive or active and the type of suspension system, as these factors may impact energy expenditure. Only the minimal necessary information to conduct the research will be requested.

Standardized On-site Evaluation. During the on-site evaluation, a trained research team member will conduct a standardized clinical examination that will include review of questionnaires, vital signs, body anthropometric measurements, and balance and physical performance testing. Demographics information including pain and socket fit comfort score will be recorded. Patients will be asked general questions about their amputation. In the event that such questioning results in an emotional response, the examiner will refrain from further questioning that may increase participant distress. Importantly, the PI will specifically train examiners in questioning with sensitivity and role-play how to handle various emotional responses during questioning. The physical examination will include

assessment of vital signs (i.e. heartrate, blood pressure, and respiratory rate) to ensure appropriateness for participation in balance and physical performance testing and assessment of height and weight for calculation of body mass index using a medical-grade scale.

1. Cumulative Illness Rating Scale (CIRS): An index of co-morbidity burden used to quantify comorbidities based on significance of the condition and medication use; co-morbidities are a known factor related to real-world walking.³⁷ Administration of the CIRS will take less than 8 minutes.
2. Residual Limb Length Measurement: Residual limb length has been proven to affect energy expenditure in individuals with lower limb amputation.⁴⁹ Increased residual limb length may contribute to a decrease in the metabolic cost of walking and an increase in comfortable walking speed due to greater preservation of lower extremity muscle mass.⁴⁹ We will include this measure to allow for control of this non-modifiable covariate during energy expenditure analyses.
3. Inspiratory Muscle Endurance Measurement: To function properly, the respiratory system relies on the strength and power of the muscles responsible for breathing air into the body (i.e. the inspiratory muscles). Inspiratory muscle dysfunction, which may result from physical inactivity, major surgery, and prolonged periods of bedrest⁵⁸, may consequently reduce an individual's ability to effectively use oxygen during activity, causing a decrease in physical activity capacity and an increase in energy expenditure during physical tasks.⁵⁹ Breathing muscle endurance will be measured using the PRO₂ Hand Built device according to the Test of Incremental Respiratory Endurance (TIRE) protocol.⁶⁰ Using this protocol, participants will be asked to exhale (breathe out) as much air as possible, then breathe into a small, handheld device as hard and as long as possible. This typically lasts between 10 and 20 seconds, and real-time feedback on breathing pressure during testing will be provided through an application on a tablet. The software will generate the maximal inspiratory pressure, MIP, as well as the sustained maximal inspiratory pressure, SMIP, and duration of inspiration. These measures will be included to comprehensively assess cardiopulmonary function and relate differences in breathing muscle endurance to oxygen consumption, physical performance, and pain.
4. Physical Performance Testing
 1. Repeated Chair Stands: Individuals are asked to stand up and sit down from a chair without using their arms as quickly as possible 5 times³⁹. This measure will be used as a functional assessment of lower extremity strength⁴⁰, which is a factor that may impact walking.
 2. Modified Clinical Test of Sensory Interaction in Balance (m-CTSIB): This measure assesses sensory input integration for balance maintenance when one or more sensory systems is compromised.⁴¹
 3. Functional Reach Test: Individuals are asked to reach forward as far as possible without moving their feet and the maximal distance reached is recorded.⁴² This test has been shown to be not only reliable and valid, but to not have a floor/ceiling effect for assessment of balance among individuals with unilateral amputations like other balance measures.⁴²
 4. Four Square Step Test (FSST): The FSST is a standing dynamic balance test used to assess lower extremity motor control.⁴³ A four-square set-up is created using canes, and participants are asked to step as quickly as possible into each square in a specific pattern, requiring steps to be taken forward, backward, and sideways to the right and left (which assesses agility).⁴³ A score of >24 seconds indicates increased fall risk in individuals with transtibial amputation.⁴⁴
 5. Figure of 8 Test: A complementary test to gait speed designed to assess both straight and curved path walking ability. Individuals are asked to walk around cones to complete a "figure-of-8".⁴⁵ Time to complete the test is recorded as well as number of steps and

the participant's ability to stay close to the cones.⁴⁵ This measure will be used to assess each individual's ability to navigate tight corridors and as a test of agility.

6. L-Test of Functional Mobility: A reliable and valid⁴⁶ clinical test where participants will be asked to stand from a chair, walk 3 meters, turn 90 degrees, walk an additional 7 meters, turn 180 degrees and return to sitting in a chair.⁴⁶ This measure will be used to assess mobility, balance, turning, and walking ability (i.e. functional mobility).

Individuals with lower-limb amputations will also complete the following:

7. Amputee Mobility Predictor: This is a reliable and valid, performance-based battery that can be used to assess functional capacity of individuals with lower-limb loss who are utilizing a prosthesis.³⁸ Tasks include those that challenge the individual's balance, transfers, and walking. Scores range from 0-47 with use of a prosthetic device, where 47 indicates a perfect score.³⁸ This measure will be used to help characterize our participants with limb amputations, since this measure is universally-used in this patient population to determine functional mobility level.

Pre-Walking Set-Up

Participants will be fit with a mobile gait analysis system (APDM Mobility Lab) that will assess gait symmetry during the over-ground and treadmill walking tests that follow. Participants will be fit with APDM Mobility Lab sensors at the following locations: sternum, posterior surface of both wrists, lumbar spine, anterior surface of both thighs, anterior surface of both lower legs (and/or the sound lower leg and the prosthetic leg), and the dorsal surface of both feet (and/or the sound foot and prosthetic foot). This will take approximately 5 minutes.

The APDM software will be used to collect spatio-temporal measurements, such as stride length and velocity, as well as three-dimensional kinematic measurements, including joint position and acceleration throughout the gait cycle and maximal toe clearance during the swing phase of gait. Information regarding trunk sway and arm swing will also be collected.

Participants will also be fit with a Polar heartrate monitor, worn around the chest on the skin, to allow vital sign monitoring during the over-ground and treadmill walking conditions. The examiner will wear the wristwatch monitoring unit during the walking bouts for ease of monitoring.

Gait Speed Pre- and Post-Walking Conditions Assessment

We will use a computerized walkway system (GaitRite) to obtain self-selected (3 trials) and fast-walking speeds (3 trials) as well as other spatiotemporal parameters of gait immediately before and after each walking condition. APDM sensor data collection will also occur during self-selected and fast walking trials over the GaitRite system. By comparing pre- and post-walking gait speeds, we may be able to determine if the participant experienced fatigue during the walking bout. This will take <3 minutes per collection; there will be 4 collections total.

Metabolic Cost Testing Procedures. Participants will have their metabolic energy expenditure (i.e. oxygen consumption) measured as they walk at various speeds within the Department of Physical Therapy. Individuals with a unilateral transtibial amputation will complete the following two tests in a randomized order (controls will complete the tests in the same order as their matched participant with a unilateral transtibial amputation):

1. 3-Stage Walking Metabolic Gas Analysis on Treadmill Test: Oxygen consumption measurements will be performed with the participant walking on a treadmill, set to three different speeds. After being fitted with the metabolic gas analysis equipment, participants will sit in a chair for five minutes to collect baseline oxygen consumption. Then, participants will walk on the treadmill at a constant speed that will be derived from the participant's self-selected gait speed as measured by the GAITRite™ walkway. In stage 1, participants will walk at 75% of their self-selected gait speed for 2.5 minutes. In stage 2, participants will walk at 100% of their self-selected gait speed for 2.5 minutes. In stage 3, participants will walk at

125% of their self-selected gait speed for 2.5 minutes. These speeds were selected based on pilot data in 44 patients with a unilateral transtibial amputation who walked on average at a mean self-selected speed of .88 m/sec (95% CI: .80, .95) if they were K3 functional level and 1.16 (1.06, 1.25) if they were K4 functional level and a mean fast gait speed of 1.15 (1.05, 1.25) and 1.53 (1.38, 1.68) if they were K3 and K4 functional level, respectively. Available safety features will be used with treadmill testing (e.g. lanyards, emergency stops).

In-between stages, participants will sit until their heart rate returns below 100 beats per minute. This methodology has been derived from prior studies with similar purposes.^{12, 25, 26} During each stage, the investigator will measure the number of steps taken using a hand tally counter; step cadence (i.e. steps/minute) will be computed from this value.

The Oxycon Mobile™ (CareFusion™, San Diego, CA) Portable VO₂ Measurement system will be used to collect expired air via a facemask to measure VO₂ uptake; this device is a lightweight, non-cumbersome machine used for portable metabolic measurement. The O₂ and CO₂ analyzers will be calibrated at the beginning of each test using standard calibration gases (16% O₂, 4% CO₂, balance nitrogen; CareFusion™, San Diego, CA). The auto calibration function will be used to calibrate volume (CareFusion™, San Diego, CA).

2. **3-Stage Walking Metabolic Gas Analysis Over-Ground Test:** Oxygen consumption measurements will be performed with the participant walking over ground in an uncarpeted corridor on a course consisting of two cones, 20-meters apart. Similar to the treadmill test, participants will be asked to walk at three different speed. After being fitted with the metabolic gas analysis equipment, participants will sit in a chair for five minutes to collect baseline oxygen consumption. Then, participants will complete the walking test in three stages. In stage 1, participants will be instructed to walk at their “slow” speed for 2.5 minutes. In stage 2, participants will be instructed to walk at their “usual, comfortable” speed for 2.5 minutes. In stage 3, participants will be asked to walk at their “brisk” speed for 2.5 minutes. In between stages, participants will sit until their heart rate returns below 100 beats per minute. This methodology has been derived from prior studies with similar purposes.^{12, 25, 26} Again, the Oxycon Mobile™ will be used to complete these measurements. During each stage, the investigator will measure the number of steps taken using a hand tally counter; step cadence will be computed from this value (i.e. steps/minute). Also, the distance the participant covers within each stage will be recorded.

Step Activity Monitoring.

At the conclusion of the on-site evaluation, all participants will be equipped with the StepWatch Activity Monitor. The activity monitor will be fastened near the ankle of the prosthesis using the straps included with the monitor (or in the case of controls, around the ankle joint of the right side).

Upon completion of the on-site evaluation, participants will be sent home with the activity monitor for a 7-day activity observation period. Participants will be instructed to perform their regular daily activities, wearing the monitor at all times that they are wearing their prosthesis. During the observation period, the activity monitor will record the number of steps the participants take. Participants will be provided with a pre-paid and addressed padded envelope and instructed to mail the activity monitor back after 7 days. Upon return of the monitors, study investigators will extract the step count data from the activity monitors. The 2 physical activity questionnaires will also be sent back re-completed (after 7 days) in these pre-paid envelopes, which will allow us to evaluate test-retest reliability of these questionnaires.

Review of Data. We will discuss and provide participants with blood pressure data, and physical performance data via written handouts (uploaded) at the conclusion of their on-site examination.

Participants with inappropriate vital signs will be managed in accordance with the policies outlined on the blood pressure screening handout; when necessary, the examiner will contact the provider.

